The cover page

The study official title:

A comparative prospective interventional study shows the impact of the clinical pharmacists' role in the emergency department in medication reconciliation upon patients' admission to reduce the medication discrepancies.

IRB number : 00012098

Date of the document:

19/12/2019

Title

A comparative prospective interventional study shows the impact of the clinical pharmacists' role in the emergency department in medication reconciliation upon patients' admission to reduce the medication discrepancies.

Background:

Hospital admission is a process which carries a high risk of medication discrepancies. This usually occur due to lack of information about patients' drug history. So one of the important roles of the clinical pharmacists in the emergency department is medication reconciliation on admission to establish a complete medication history list .Many studies found that medication reconciliation will reduce medication errors and achieve significant clinical and economic outcomes.

Aim of the study:

The aim of the study is to calculate the total number of medication discrepancies recorded by the clinical pharmacists after medication reconciliation, to classify these medication discrepancies using Medications at Transitions and Clinical Handoffs (MATCH) Toolkit for Medication Reconciliation, to calculate the proportion of the patients detected with one or more medication discrepancies and to calculate the total number of complete medication history lists established after the clinical pharmacists medication reconciliation.

Patients and methods:

Approval of the medical ethics committee of Alexandria faculty of Medicine will be taken.

.No informed consent will be taken as medication reconciliation is considered to be an essential role of clinical pharmacists upon patients' admission.

It is comparative prospective interventional study during the period from 1 January 2020 to 29 February 2020 in emergency department in Alexandria Main University Hospital.

-Three/ four well trained emergency clinical pharmacists will start medication reconciliation on admission during the morning and evening shifts.

-A full diseases and preadmission medications history will be taken from the patients or the family through interviews, revising previous prescriptions and hospital records.

- Preadmission medication history will include medications trade names, doses, frequency and rout of administration and treatment duration and also will include the consumption of vitamins or herbs.

- The detection of medication discrepancies will be done through a comparison between each patient drug history already presented in the profile and drug history taken by the clinical pharmacists.
- Establishment of a complete medication history list in each patient profile and discuss it with the physicians to rearrange the treatment plan will be done.

Inclusion criteria:

- 1- Patients with one or more chronic disease / drug.

Exclusion criteria:

Patients who cannot communicate or have no family members.

Outcomes:

- 1- to calculate the total number of medication discrepancies recorded by the clinical pharmacists after medication reconciliation,
- 2- to classify the medication discrepancies using Medications at Transitions and Clinical Handoffs (MATCH) Toolkit for Medication Reconciliation.
- 3- to calculate the proportion of the patients detected with one or more medication discrepancies
- 4- to calculate the total number of complete medication history lists established after the clinical pharmacists medication reconciliation.

Results:

The results obtained in this study will be tabulated, correlated and statistically analyzed.

DISCUSSION

The results of this work will be analyzed and discussed in the view of the achievement of the aim, their significance and comparison with other studies carried out by other investigators.

Medications at Transitions and Clinical Handoffs (MATCH) Toolkit for Medication Reconciliation

Agency for Healthcare Research and Quality

Category	Description
A	No error, capacity to cause error
B	Error that did not reach the patient
C	Error that reached patient but unlikely to cause harm (omissions considered to reach patient)
D	Error that reached the patient and could have necessitated monitoring and/or intervention to preclude harm
E	Error that could have caused temporary harm
F	Error that could have caused temporary harm requiring initial or prolonged hospitalization
G	Error that could have resulted in permanent harm
H	Error that could have necessitated intervention to sustain life
I	Error that could have resulted in death

References:

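### Does confining reconciliation to the morning and evening shifts leave the proportion of patients with a discrepancy without a defined population?

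*Protocol*

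**What the plan says.** The protocol's Patients and methods section places the study in one department over a fixed period: "during the period from 1 January 2020 to 29 February 2020 in emergency department in Alexandria Main University Hospital". The work is done by "Three/ four well trained emergency clinical pharmacists", who "will start medication reconciliation on admission during the morning and evening shifts". No clock hours or roster are given. The section does not mention a night shift, and it does not say whether patients arriving outside the two shifts are left out or picked up later.

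The inclusion criterion is "Patients with one or more chronic disease / drug" and the exclusion criterion is "Patients who cannot communicate or have no family members". Neither refers to time of arrival.

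Discrepancies are found by a "comparison between each patient drug history already presented in the profile and drug history taken by the clinical pharmacists". The third outcome is "to calculate the proportion of the patients detected with one or more medication discrepancies". The text does not add whether this means all eligible admissions, those in the covered shifts, or those actually reconciled.

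**The concern.** Read side by side, the eligibility criteria are open to any suitable patient at any hour, while the procedure is delivered only in two named shifts. If those shifts leave part of the day uncovered, some eligible patients are never assessed. Outcome 3, and the severity classification in outcome 2, would then describe only part of the eligible population.

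Night arrivals may differ from day arrivals. They may be sicker, or have fewer relatives or old prescriptions at hand, so their discrepancy rate could differ too. The protocol plans no log of eligible patients who were not seen, so a reader could not later work out how large the missed share was. Because the protocol also intends to compare its results with other studies, it matters whom the proportion describes.

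**Working it through.** The protocol states no expected proportion, sample size or coverage figure, so there is nothing to reproduce. The check has two parts: what the text fixes, and how large a gap could be under stated assumptions.

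**What the text fixes.** Four elements of the sampling frame are given: site, calendar period, eligibility and shifts. The period is 31 + 29 = 60 days, or 60 × 24 = 1,440 hours. The elements left open are the shift hours, the handling of other arrivals, and whether every eligible patient in a covered shift is taken. The method of detection narrows the denominator further. It needs two histories per patient, the one already in the profile and the one the pharmacist takes. A patient no pharmacist has seen has no second history and cannot be classed as with or without a discrepancy. The proportion can be computed only among reconciled patients.

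**Size of a gap if the figure were read as department-wide.** Let s be the share of eligible arrivals outside the covered shifts, and p_c and p_u the true proportions with a discrepancy in covered and uncovered arrivals. The all-arrivals proportion is (1 − s)p_c + s·p_u, so the covered-shift figure differs from it by

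gap = s × (p_c − p_u).

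The protocol gives none of these inputs. Everything below is assumed.

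For s, take u uncovered hours per day and a night arrival rate r times the day rate. Then s = r·u / (r·u + 24 − u).

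| Uncovered hours per day | Hours over 60 days | s at equal rates (r = 1) | s at half the day rate (r = 0.5) |
|---|---|---|---|
| 0 | 0 | 0 | 0 |
| 8 | 480 | 8/24 = 0.33 | 4/(4 + 16) = 0.20 |
| 12 | 720 | 12/24 = 0.50 | 6/(6 + 12) = 0.33 |

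The gap in percentage points is then:

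| s | Difference 0 | Difference 10 | Difference 20 |
|---|---|---|---|
| 0 | 0 | 0 | 0 |
| 0.20 | 0 | 2.0 | 4.0 |
| 0.33 | 0 | 3.3 | 6.7 |
| 0.50 | 0 | 5.0 | 10.0 |

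Put the other way, a 5-point gap needs a true difference of 5/0.20 = 25, 5/0.333 = 15 or 5/0.50 = 10 points at these three missed shares.

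With no assumption about unseen patients, the bounds on the all-arrivals proportion are (1 − s)p_c to (1 − s)p_c + s. For an assumed 50% among those seen, that is 40% to 60% at s = 0.20 and 33% to 67% at s = 0.33.

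**What the other outcomes need.** The comparison of histories is made within each patient, so who else was or was not seen does not bias it. Outcomes 1 and 4 are counts of what the pharmacists recorded and set up. They are correct as counts whatever the coverage, although they cannot be scaled to the whole department without knowing it.

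**The case for a change.** The strongest case for a change is that coverage is a matter of conduct, not of analysis. An analysis plan can choose a denominator, but it cannot recover patients whom nobody logged. With three or four pharmacists and no roster, eligible patients may be missed even within the covered shifts, so *admitted in a covered shift* and *actually reconciled* are not the same group. A shift field and a simple count of eligible patients not seen would cost little over 60 days and would let a reader put limits on the missed share.

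Much of this stands. The hours are missing, the denominator is not spelled out, and such a log would be good practice. It does not show that the plan goes wrong as written. An uncovered night period is an inference: the two shifts could span 24 hours, and the sentence could also describe when the pharmacists work without ruling out that overnight arrivals are reconciled in the morning. The outcomes describe what the pharmacists find in the patients they reconcile, and no round-the-clock prevalence is promised. The obvious remedy, taking eligible patients admitted in the covered shifts as the main estimate, is how the text already reads. Adding overnight patients at the next morning shift would bring in people selected for still being present, with a profile history that may have changed. They would have to be reported apart and would leave the main estimate untouched.

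**Conclusion.** No change to the plan is needed. The shift coverage and the denominator of outcome 3 are incompletely described, but the frame is not unknown. Followed as written, the plan gives a valid descriptive proportion for eligible patients reconciled in the morning and evening shifts of one department over 60 days. An analyst would use that denominator without prompting, because no other can be computed from the data collected.

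What remains is a limit on generalisation. Its size cannot be determined from the document and may be zero. The 0 to 10 point range rests wholly on the assumed inputs, and its upper end needs half of eligible arrivals missed together with a 20-point difference between those seen and those missed. The sensible course at reporting is to state the shift hours, give the number of eligible patients not seen if it is known, and word the conclusions for the admissions actually covered.

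### Outcome 1 is a raw total of discrepancies; stating it per patient and per 100 medications would let it be compared with other studies

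*Protocol*

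**What the plan says.** The Protocol's Aim opens with "The aim of the study is to calculate the total number of medication discrepancies", and item 1 under Outcomes repeats it: "to calculate the total number of medication discrepancies recorded by the clinical pharmacists after medication reconciliation". Neither place gives a denominator.

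Patients and methods runs the study "during the period from 1 January 2020 to 29 February 2020", with three or four pharmacists on two daily shifts and no target number of patients. The inclusion criterion asks for at least one chronic disease or drug and sets no upper limit.

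Discrepancies are found by a "comparison between each patient drug history already presented in the profile and drug history taken by the clinical pharmacists", so the work is done patient by patient. On content, "Preadmission medication history will include medications trade names, doses, frequency and rout of administration and treatment duration". The same section plans a full drug list for the profile of every patient.

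Two other outcomes bear on the point. Item 3 is "to calculate the proportion of the patients detected with one or more medication discrepancies". Item 4 is "to calculate the total number of complete medication history lists established after the clinical pharmacists medication reconciliation", which is again a total. The Discussion paragraph says the results will be compared with those of other investigators.

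**The concern.** A total is the product of three things: how many patients were reconciled, how many drugs each had, and how often a drug was discrepant. The first depends on a calendar window and staffing, the second on case mix. A reader who sees a high total cannot tell whether admission histories were poor, the department was busy, or the patients took many drugs.

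At stake is the planned comparison with other studies, which will have seen different numbers of patients on different numbers of drugs. Because the protocol itself fixes the measure as a total, this is not simply a detail left to an analysis plan.

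**Working it through.** The protocol states no sample size, discrepancy rate or drug count, so there is no figure to reproduce. The values of N, m and r below are assumptions for illustration.

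**Identity.** Expected total = N × m × r, where N is patients reconciled, m is medications per patient and r is discrepancies per medication. The study window is 31 + 29 = 60 days, with no N stated.

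**Same quality, different totals (r = 0.20).**
- N = 150, m = 3: 150 × 3 × 0.20 = 90
- N = 400, m = 8: 400 × 8 × 0.20 = 640

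The ratio is 640 / 90 = 7.1, with no change in r. At equal N, going from 3 to 8 drugs alone multiplies the total by 8 / 3 = 2.67.

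**Same total, different situations.**

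| N | m | r | Total | Per patient | Per 100 medications |
|---|---|---|---|---|---|
| 400 | 4 | 0.20 | 320 | 320/400 = 0.8 | 320/1,600 = 20 |
| 200 | 8 | 0.20 | 320 | 320/200 = 1.6 | 320/1,600 = 20 |
| 200 | 4 | 0.40 | 320 | 320/200 = 1.6 | 320/800 = 40 |

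Knowing N separates the first row from the other two. Only the medication count separates the second from the third. The two measures together distinguish all three rows.

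**What the other outcomes supply.** Outcome 3 needs the number of patients, and outcome 4 equals that number if every reconciled patient gets a list, as Patients and methods plans. So the mean per patient is total / N. Outcome 3 does not itself measure burden: if 100 of 200 patients are affected it is 50%, whether each has one discrepancy (100/200 = 0.5 per patient) or four (400/200 = 2.0). No listed outcome supplies the number of medications.

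**Choice of medication denominator.**
- Profile {A, B, C}, pharmacist's list {B, C, D, E}: three discrepancies (A extra; D and E missing). Over all distinct drugs on either list, 3/5 = 60 per 100; over the pharmacist's list alone, 3/4 = 75.
- Profile {A, B}, list {C}: 3/3 = 100 against 3/1 = 300.
- Profile {A}, empty list: 1/1 = 100 against an undefined value.

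The union of the two lists stays defined in all three examples.

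**Counting unit.** If 160 drugs are discrepant and half differ in two fields, the count is 160 by drug, or 80 × 1 + 80 × 2 = 240 by difference. The unit must therefore be named with the rate.

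**The case against.** The strongest reply is that outcome 1 does not stand alone. Outcome 3 is a proportion of patients, so N has to be known. A list is planned for every profile, so outcome 4, as planned, counts the reconciled patients. Dividing outcome 1 by N is something a reader can do. This stands, and it removes any claim that the study lacks a patient denominator.

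A second reply is that the protocol never names the quality of the profile history as its target. As a description of what the pharmacist service finds, a total is legitimate, and so is a per-patient burden that includes the number of drugs. This also stands. A reader might infer that only the rate per drug is meaningful and that the total is uninterpretable. The document does not support that, because it names no such target and labels no outcome as primary.

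Third, if both drug lists are kept for each patient, medication counts can be made afterwards. That is true, but the protocol does not say that such counts will be kept or reported.

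Finally, the interval method and the rule for several differences on one drug can be settled in an analysis plan, which is not at hand. Their absence is not a defect here. A rule that always counts a drug once would also sit badly with outcome 2, because two differences on one drug may fall in different MATCH categories. The fix has to respect that.

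**Conclusion.** The point holds in a limited form. Outcome 1 is fixed as a raw total that moves with patients seen and drugs per patient, so it does not serve the planned comparison with other studies. The per-patient mean is recoverable from what the protocol already requires; the rate per medication is recoverable only if drug counts are kept.

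The direction follows from the definition. The sizes, about 7-fold between the extremes shown, rest wholly on the assumed 150 to 400 patients, 3 to 8 drugs each and 20 discrepancies per 100 drugs. A reader might infer that the study cannot describe discrepancies at all or that a stated number is wrong. Neither follows: outcome 3 has a proper patient denominator, and there is no stated figure to be in error. The weight is minor to moderate.

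**What to change.** Restate outcome 1, in the Aim and under Outcomes, as two measures:
- (a) the mean number of discrepancies per reconciled patient;
- (b) discrepancies per 100 medications compared, where the denominator is all distinct medications on either the profile history or the pharmacist's history. Sum numerator and denominator over patients before dividing.

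Give 95% confidence intervals that treat the patient as the unit, since discrepancies within a patient are not independent. The method can be left to the analysis plan. Keep the raw total as a descriptive line beside the number of patients reconciled. Outcome 3 stays as it is.

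Use for outcome 1 the same counting unit that outcome 2 classifies, and state it. If (b) is instead defined by counting each discrepant medication once, say so. It then lies between 0 and 100, and outcome 2 can still classify each difference separately.

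The cost is small. Both histories are already compared for each patient, so no new data are needed. There is slightly more analysis work, and discrepancy and medication counts must be kept per patient.
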